The above testing suggests that the NEMO™ Gauge is safe for human use. An IRB approved trial is currently underway at a U.S. academic medical center (per Ciel Medical, the manufacturer). This prospective trial studies the use of the NEMO™ Gauge in up to 50 intubated patients undergoing bronchoscopy. Main outcomes include confirmation of accurate measurement of the ETT tip-to-carina distance using the NEMO™ Gauge compared to bronchoscopy measurement, and assessment of mucosal damage during the use of the NEMO™ Gauge. In this study, a bronchoscopy was performed after the use of the NEMO™ Gauge. An interim analysis of 17 patients showed 94% accurate measurement using NEMO™ Gauge (2-5cm from the carina). In one patient (6%) the ETT tip was determined to be inside the 2-5 cm range using the NEMO™ Gauge but was actually at 5.5cm. Eight (8) patients displayed signs of mild mucosal irritation and nine (9) patients showed no irritation after use of the device. No adverse events have been reported to date (ongoing study, unpublished results provided by Ciel Medical).

Specific Aims:

The aim of this study is to investigate the NEMO™ Gauge's ability to accurately and safely determine ETT position, and if needed, guide repositioning of the ETT into the correct position, compared with standard chest radiography.

Inclusion Criteria:

1. Adult patients \geq 18 years of age admitted to the intensive care unit (ICU)
2. Patients who have been intubated or at high risk of being intubated, requiring confirmation of ETT position after intubation as determined by the clinical team
3. Endotracheal tube size 7.0 mm to 8.5 mm in diameter

Exclusion Criteria:

1. Patients with active hemoptysis
2. Patients with known tracheal or bronchial masses prior to endotracheal intubation
3. Patients with known tracheal or bronchial abnormalities requiring surgical repair

4. Patients with ongoing hypoxemia (defined as $\text{SaO}_2 < 85\%$) after endotracheal intubation
5. Any individual involuntarily confined or detained in a penal institution

Study Procedure:

Study physicians will be trained on the use of the NEMO™ Gauge device by viewing a video tutorial, reading the manufacture instructions provided with the device, and performing an ETT position confirmation with the NEMO™ Gauge on a trachea simulation model (mannequin).

[figure not shown]

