Patients who are intubated and meet enrollment criteria will be selected for the study procedure (Figure 6). After intubation, the patient will be positioned for the chest radiograph by standard practice. Prior to obtaining the chest radiograph, the NEMO™ Gauge will be used to determine proper tube positioning and should it be necessary the ET tube will be repositioned as per the NEMO™ Gauge's manufacture instructions. Additionally, the operator will auscultate the patient's lung for bilateral breath sounds.

Immediately after use of the NEMO™ Gauge and confirmation of bilateral breath sounds, a chest radiograph will be completed. The distance from the tip of the ET tube to the carina will be measured on the radiograph and will be recorded. Based on current clinical practice⁸⁻⁹, the ET tube will be considered a malposition if it is located less than 2 cm from the main carina, more than 5 cm from the main carina, in the right main stem bronchus, or in the left main stem bronchus.

If the ET tube is considered in a malposition as determined by the chest radiograph, it will be re-adjusted as per standard practice, now without the NEMO™ Gauge. The distance that the ET tube is adjusted will be recorded.

Demographics, diagnostic data, ventilator settings, and ongoing treatments will be recorded. The reason for intubation, ETT size, ETT position, and ETT adjustments will also be recorded. Any complication as a result of the intubation, ETT positioning, and/or NEMO™ Gauge will be recorded.

Figure 6: An outline of the Study Procedure

Primary Outcome:

The percentage of correct ETT position as confirmed by chest radiographs after using the NEMO™ Gauge.

Sample Size / Number of Subjects:

Based on our literature review, correct ETT position after intubation are observed in approximately 91% of patients when verified by standard chest radiograph (the null hypothesis). We hypothesize that use of the NEMO™ Gauge to detect ETT position and make necessary adjustments will result in 98% correct ETT position.

Using a one-sided binomial test, a sample size of 68 patients will detect an increase in ETT correct position of 7% with the use of the NEMO™ Gauge, having a power of 0.84 and a significance level of 0.0492.

Statistical Analysis:

Simple descriptive analysis will be performed, including the percentage of correct ETT position and any complication after the use of the NEMO™ Gauge. See also Interim Analysis below.

Study Duration:

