The enrollment criteria for this study consist of patients requiring or at high risk for requiring intubation and placement on invasive mechanical ventilation. These patients may have altered sensorium and may not be able to provide written informed consent at the time of meeting study enrollment criteria. In such case informed consent may be obtained from a legal authorized representative (LAR).

Patients admitted to the ICU service (irrespective of physical location in the hospital) or their LAR will be presented information about this study and given an opportunity to participate after all their questions have been answered. No study procedures will occur prior to their written informed consent. The consent process is as follows in the figure:

Since it is impossible to know in advance which patients will require intubation and mechanical ventilation in the ICU, we will obtain prospective written informed consent shortly after ICU admission in all patients who may or may not yet require intubation. Not all ICU admitted patients will require intubation during their ICU stay. Thus, we anticipate that only a portion of consented patients may ultimately have study procedures performed on them.

Potential Risks:

Endotracheal intubation is associated with a significant number of adverse events, some of which are serious. These events related to intubation are relatively common and have been studied extensively. Our study is NOT examining the intubation itself, but rather the correct adjustment (if any) of the endotracheal tube AFTER intubation has already occurred. With this in mind, one of the study investigators, not directly involved in the patient care or study procedures will make a determination whether or not events surrounding the intubation are related to intubation vs. to the NEMO™ Gauge.

Nearly all intubated patients undergo suctioning of airway secretions right after intubation and on a regular, as needed basis, multiple times each day for as long as they remain intubated. Suction catheters frequently cause irritation and occasionally bleeding from the tracheal mucosa. The risks associated with the use of the NEMO™ Gauge are approximately similar to the risks associated with routine endotracheal suctioning.

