There are always unforeseen risks beyond those of routine endotracheal suctioning; however, we believe the incremental risks from use of this device are minimal. This is based on the pre-clinical device testing (described above) that has occurred as well as to the clinical experience with the device since it has been on the market. The major potential risk associated with this device is the possibility of minor tracheal damage from contact with the tracheal wall. There is a theoretical possibility that the forces exerted on the tracheal wall may cause local mucosal damage during use. The manufacturer has conducted technical performance testing in both live porcine models and bench models to show similar exertion forces as other commercially available products, with favorable results. However, if signs of tissue damage are apparent during use, the NEMO™ Gauge will be removed and the investigators will evaluate the severity of the adverse event and, as needed, will initiate immediate corrective measures. The investigators will determine if any adverse event is attributed to the NEMO™ device. Any serious and/or unexpected adverse device events will be reported to the IRB at the respective site and appropriate federal agencies per their requirements (see Data Safety Monitoring below).

Plan for Communication among IRB:

Any serious adverse events (SAE) associated with this trial will be reported to the local institution IRB immediately in accordance with local reporting regulations. Other non-serious adverse events will be recorded in the local study records and reported to the IRB at the time of continuing review.

Data safety monitoring:

We will follow the FDA guidance, “Medical Device Reporting for User Facilities”: (<http://www.fda.gov/downloads/MedicalDevices/DeviceRegulationandGuidance/GuidanceDocuments/UCM095266.pdf>).

Table 1 - Summary of MDR Reporting Requirements

REPORTER	REPORT WHAT?	TO WHOM?	WHEN?
User Facility	Deaths	FDA and Manufacturer	Within 10 work days
	Serious injuries*	Manufacturer FDA only if manufacturer unknown	Within 10 work days
	Semiannual report of deaths and serious injuries	FDA	January 1 and July 1

*Serious injuries – an injury or illness that is 1) life threatening; 2) results in permanent impairment of a body function or permanent damage to a body structure; or 3) necessitates medical or surgical intervention to preclude permanent damage or impairment.

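### Potential Risks calls mucosal damage theoretical and omits the plan's own finding of irritation in 8 of 17 patients, an effect the general complications field cannot be expected to capture

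*Combined protocol and SAP*

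**What the plan says.** - **Potential Risks**, on the mucosa: "There is a theoretical possibility that the forces exerted on the tracheal wall may cause local mucosal damage during use". The same section calls the incremental risk minimal, on the strength of pre-clinical testing and experience since marketing. The sentence just before the quoted one names minor tracheal damage as the main potential risk. Earlier, the section compares the gauge with routine suctioning, which it says often irritates the mucosa and sometimes makes it bleed.
- **Previous Device Testing**, on the ongoing study in intubated patients: its main outcomes are measurement accuracy "and assessment of mucosal damage during the use of the" gauge. On method: "In this study, a bronchoscopy was performed after the use of the" gauge. On results: "An interim analysis of 17 patients showed 94% accurate measurement", and "Eight (8) patients displayed signs of mild mucosal irritation and nine (9) patients showed no irritation after use of the device". The same paragraph says that no adverse events had been reported.
- **Specific Aims**: the trial is to investigate the gauge's "ability to accurately and safely determine ETT position".
- **Study Procedure**: "Any complication as a result of the intubation, ETT positioning, and/or NEMO™ Gauge will be recorded". The steps after gauge use are auscultation and a chest radiograph.
- **Data Collected**: a general entry for complications, where there are any, and an investigator's judgement of whether they relate to the gauge. No mucosal finding is listed.
- **Statistical Analysis**: complications are summarised descriptively.

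**The concern.** There are two linked problems.

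First, the risk statement treats as hypothetical something for which the protocol already holds human data. A study that set out to assess mucosal damage found signs of irritation in almost half of its patients. Potential Risks argues from other evidence and leaves that result out. A reader who relies on that section alone, or on consent text that repeats it, would not learn of it.

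Second, safety is part of the aim, but nothing in the listed data is directed at the mucosa. Neither auscultation nor a radiograph shows it. A mucosal effect enters the record only if someone happens to notice it and regards it as a complication. A low complication count would then say little about mucosal effects. The mid-study report to the DSMB draws on the same adverse-event record.

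**Working it through.** **Step 1: check the human figure.** From Previous Device Testing, 8 patients had irritation and 9 had none. 8 + 9 = 17, which matches the interim denominator. The accuracy figures agree with it too: 16/17 = 94% and 1/17 = 6%.

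**Step 2: rate and precision.** 8/17 = 0.471, or 47%. The exact (Clopper-Pearson) 95% interval for x = 8, n = 17 is:
- lower limit = 2.5% quantile of Beta(x, n − x + 1) = Beta(8, 10) = 0.230
- upper limit = 97.5% quantile of Beta(x + 1, n − x) = Beta(9, 9) = 0.722

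The interval is therefore 23% to 72%. It is wide, but even its lower end is not a rate one would call theoretical.

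**Step 3: what the rate measures.** It is the proportion with irritation seen at bronchoscopy after gauge use, in patients who were already intubated. The summary describes no inspection before gauge use. The 47% therefore combines any effect of the gauge with effects of the tube and of suctioning, and the documents do not allow these to be separated.

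**Step 4: would a general field capture it?** In the 17-patient study, irritation was looked for with a bronchoscope and found in eight patients, yet the adverse-event count was zero. In the present trial the mucosa is not inspected and irritation has no item of its own. If irritation that had been seen was not counted as an adverse event there, irritation that is not seen cannot be expected to appear under complications here.

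**Step 5: what a zero count would mean.** With 0 complications in 68 patients, the exact upper limit is 1 − 0.05^(1/68) = 4.3% (one-sided 95%) or 1 − 0.025^(1/68) = 5.3% (two-sided 95%). Either limit applies to complications that were noticed and recorded. Neither limits irritation that only a bronchoscope would show.

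**Step 6: effect on the design.** The plan's only design calculation reproduces. With success defined as at least 66 of 68 correct positions, the exact binomial gives a significance level of 0.0492 at 91% and a power of 0.8446 at 98%, against the stated 0.0492 and 0.84. Nothing in this point changes it.

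**The case against.** The other side has a good case on several matters.

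- **Irritation is not damage.** The human report says mild irritation, and the risk section says damage. The tension depends on reading irritation as a sign of damage. That reading has support, because the irritation was reported from a study with mucosal damage as a main outcome, but it remains a reading.
- **The risk is partly disclosed.** The section names minor tracheal damage and likens the gauge to suctioning, and minimal refers to risk beyond suctioning. The 8 and 9 patients are printed in full elsewhere in the protocol. A reader might infer that the finding is hidden; the documents do not support that. The suctioning comparison, however, itself sits poorly with the word theoretical.
- **Complications are not left to chance altogether.** The data list applies to every subject, an investigator outside the patient's care judges relatedness, and adverse events go to the DSMB. The general field would record damage that someone noticed. The gap is the lack of active, predefined ascertainment.
- **Visible blood is a different endpoint.** The irritation report mentions no bleeding, and suctioning or intubation can cause bleeding. This stands, and it limits what the added items can be said to measure.

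A reader might also multiply 8/17 by 68 and infer 32 missed cases, or set the 5.3% limit against 47% as a measure of under-reporting. Neither holds. The first carries a bronchoscopic rate with no pre-gauge comparison into a trial without bronchoscopy. The second compares two different endpoints. Nor do the documents say that few complications will be taken as proof of safety: they set no safety criterion.

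**Conclusion.** The point holds in a limited form. Potential Risks should not call the mucosal effect theoretical while omitting an observed 8 of 17 (47%, exact 95% CI 23% to 72%). As listed, the data cannot be expected to capture that effect, so a low complication count could not support the safety part of the aim for the mucosa.

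This rests on three assumptions. Irritation is taken as relevant to mucosal damage, as the cited study's outcome implies. The case report form is taken to follow the list under Data Collected, since the form itself is not in the documents. Consent text matters only if it repeats the risk wording, and it could not be seen.

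It would go too far to infer that the gauge injures about half of patients. The finding is mild irritation, and the share due to the gauge is unknown. The change is worth making because it is cheap and bears on a stated aim. It does not touch the primary outcome, sample size, significance level or power.

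**What to change.** 1. **Risk statement.** In Potential Risks, and in any consent text that repeats it, replace the theoretical wording with the observed result. For example: *In an ongoing study, bronchoscopy after gauge use showed mild mucosal irritation in 8 of 17 patients (47%, exact 95% CI 23% to 72%); there was no comparison before gauge use, so the part due to the gauge is unknown.*
2. **Solicited items.** Add required yes/no items to the case report form for visible blood on the gauge at withdrawal and for fresh blood in the first routine suction after use. Where suction was also done before use, record the same item then, as the patient's own baseline. The plan says: "Nearly all intubated patients undergo suctioning of airway secretions right after intubation". No new procedure is therefore needed. Report the counts with exact intervals, as clinically visible bleeding and not as a measure of irritation.
3. **Scope of the safety conclusion.** Under Statistical Analysis, state that the trial does not inspect the mucosa, cannot estimate the irritation rate, and limits its safety conclusion to clinically visible events.

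The cost is a few tick-boxes and some lines of text, with no added procedure or staff. Attribution will be imperfect, because suctioning and intubation can also cause bleeding and the baseline will be missing where no suction preceded gauge use. The risk statement and the safety conclusion will both read less favourably.

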All deaths and serious injuries at a study site that are determined to be caused by or contributed by the NEMO™ Gauge shall be reported by the site PI, following the site’s institutional process for medical device reporting to the FDA; i.e. the same process used for any FDA-approved medical device. The timeline for reporting should follow the FDA requirements as in Table 1 above.

In addition to the required FDA reporting, the site PI will also submit the report (FDA Form 3500A) to the study lead investigator (SLI) within 72 hours of the event. The SLI will then notify all study sites and the IRB at Loma Linda University of such event.

If the site PI did not voluntarily report the event to MedWatch, the SLI will report such event to MedWatch:

<https://www.accessdata.fda.gov/scripts/medwatch/index.cfm?action=reporting.home>. Such voluntary reporting to MedWatch will potentially be beneficial to society regarding the risk of the NEMO gauge device.

The SLI will also report other deaths or serious injuries to the FDA, MedWatch, and the IRB at Loma Linda University that have not been reported by the individual sites.

Interim Analysis:

A Data Safety Monitoring Board (DSMB) will be organized to provide oversight of the study. The DSMB will consist of two (2) independent intensivists and one (1) biomedical ethicist

unrelated to the study. [name], PhD, Vice-President for Mission and Culture at Loma Linda University, will be invited as our ethicist on the DSMB.

The SLI will organize a mid-study interim analysis at one-half enrollment (34 out of total 68 subjects). Data will be analyzed by the study team (including the SLI, site PI's, and statistician). Results of the analysis will include the percentage of correct endotracheal tube position and any adverse events (including serious injuries and deaths) from the use of the NEMO™ Gauge.

The results of the mid-study analysis will be submitted to the DSMB for review. Depending on the number and severity of adverse events, the SLI and DSMB will determine whether enrollment at all study sites should cease.

The SLI will also perform an event related interim analysis throughout the study period if a death or serious injury is determined to be caused by or contributed by the NEMO gauge. The event will be reported to the IRB at Loma Linda University. In such situation, the SLI and DSMB will determine whether enrollment at all study sites should cease until a complete review of the event is completed.

References:

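### The mid-study report need only show the DSMB events attributed to the gauge; listing every recorded complication with its relatedness assessment would be a cheap improvement

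*Combined protocol and SAP*

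**What the plan says.** The Interim Analysis section plans a "mid-study interim analysis at one-half enrollment (34 out of total 68 subjects"). The study team, including the study lead investigator and the site investigators, analyzes the data. The results will include "the percentage of correct endotracheal tube position and any adverse events (including serious injuries and deaths) from the use of the NEMO™ Gauge", and they are then submitted to the DSMB. The study lead and the DSMB decide whether enrollment stops: "Depending on the number and severity of adverse events". Outside that look, an event-related analysis takes place "if a death or serious injury is determined to be caused by or contributed by the NEMO gauge".

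Two statements under Potential Risks govern attribution. For events around the intubation, "one of the study investigators, not directly involved in the patient care or study procedures will make a determination" on whether intubation or the gauge was responsible. More generally, "The investigators will determine if any adverse event is attributed to the NEMO™ device".

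Collection is wider than the report. Study Procedure records complications of the intubation, the tube positioning or the gauge. Data Collected adds an investigator's assessment of whether each was related to the gauge. Statistical Analysis describes complications following gauge use, without a causal condition, and refers the reader to Interim Analysis.

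Serious events are also reported elsewhere. Under Plan for Communication among IRB, "Any serious adverse events (SAE) associated with this trial will be reported to the local institution IRB immediately". Under Data safety monitoring, gauge-attributed deaths and serious injuries go through the FDA device-reporting process and to the study lead, who informs all sites and the Loma Linda IRB. That section adds: "The SLI will also report other deaths or serious injuries to the FDA, MedWatch, and the IRB at Loma Linda University", limited to those the sites have not already reported. None of these sentences names the DSMB as a recipient.

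**The concern.** The board is asked to weigh how many adverse events there were and how severe they were. The required report, however, contains only events that the study's own investigators have already ascribed to the device. A board that sees only one side of a classification cannot check it.

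Attribution is difficult in this trial. There is no control arm, and the gauge is used shortly after intubation. Potential Risks describes intubation events as fairly common and says that routine suctioning irritates the mucosa and sometimes makes it bleed. A gauge injury could reasonably be taken for either. If it were, and the report held only the required minimum, the DSMB could help decide on enrollment without knowing of the event.

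**Working it through.** This is mainly a matter of reading the text. First, the passages side by side:

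| Step | Section | Which events are covered |
|---|---|---|
| Recording | Study Procedure; Data Collected | Complications of intubation, positioning or gauge, with relatedness |
| Descriptive analysis | Statistical Analysis | Complications that follow gauge use (a condition on time) |
| Mid-study report to the DSMB | Interim Analysis | Adverse events resulting from gauge use (a condition on cause) |
| Event-triggered review | Interim Analysis | Deaths and serious injuries determined to be caused or contributed to by the gauge |

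The condition changes from time to cause at the point where data go to the board. The information needed for a full listing already exists one step earlier.

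Next, trace three kinds of event to the DSMB:

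1. *Classed as gauge-related.* Must appear in the mid-study report if it occurs before the look. If it is a death or serious injury, it also starts the event-triggered review. No gap.
2. *Non-serious, classed as intubation-related.* Recorded on the case report form. Non-serious adverse events go to the IRB at continuing review. No sentence requires the event to reach the DSMB.
3. *Death or serious injury, classed as intubation-related.* Does not start the event-triggered review and need not be in the mid-study report. It may reach an IRB, the FDA or MedWatch through the routes above, but the DSMB is not named on any of them.

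The arithmetic on timing: the look is at 68 × 1/2 = 34 patients, so 68 − 34 = 34 patients (34/68 = 50%) are enrolled after it. No later look is scheduled. For those patients the only stated route to the DSMB is the event-triggered review, which depends on attribution.

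Last, a check that the design figures are not involved. With success defined as at least 66 of 68 correct positions, the exact binomial tail is 0.0492 at a true rate of 0.91 and 0.845 at 0.98. These reproduce the stated significance level of 0.0492 and power of 0.84. A change to the safety listing alters none of them.

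**The case against.** The strongest reply is that the plan already permits what is asked. The listed content is a minimum. Statistical Analysis uses the wider wording and points to Interim Analysis, so a full listing is a fair reading of the two together. The DSMB is set up to oversee the study, and nothing stops it from asking for more. All of this stands. A reader might infer that the sections contradict each other or that the board is barred from seeing intubation events; the documents support neither reading.

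There are also real safeguards. The assessor of events around the intubation is outside the patient's care and the study procedures. The trigger covers contribution as well as causation, and its sentence does not say who makes the determination; that it is the investigators is an inference from Potential Risks. Serious events go to IRBs and, by some routes, to the FDA and MedWatch, and the study lead, who shares the enrollment decision, handles several of those reports. A reader might infer that a serious event judged unrelated to the gauge goes unreviewed by anyone; that is not supported. The gap concerns only what the DSMB must be shown.

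The only clinical data cited, under Previous Device Testing, are 17 patients with mild mucosal irritation in eight and no reported adverse events. That gives no reason to expect many serious events, and it gives no rate of misclassification.

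What remains is that the fuller report depends on someone choosing to prepare it or the board thinking to ask for it, although the data are already collected.

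**Conclusion.** The point holds as a cheap improvement, to be considered rather than required. As written, the mid-study report may omit complications that investigators classed as intubation-related, and the event-triggered review depends on attribution to the gauge as well. The one firm figure is that 34 of 68 patients (50%) are enrolled after the only scheduled look.

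The conclusion rests on reading the report's content as a minimum that could be followed literally. It does not assume that any event will be misclassified. It is tempting to put a probability on a missed event, or to compare upper confidence limits with and without one. The documents give no event rate, no misclassification rate and no numeric stopping threshold, so such figures would rest on assumption and would feed no rule in the plan.

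**What to change.** In Interim Analysis, keep the correct-position percentage and replace the adverse-event part of the report content with wording such as:

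> The mid-study report to the DSMB will list all complications recorded on the case report form, including deaths and serious injuries recorded there, regardless of attribution, with the relatedness assessment shown for each and, where known, whether onset was before or after use of the gauge.

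This also brings the section into line with Statistical Analysis. The way the enrollment decision is made stays as the plan states it.

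Cost: one sentence. Complications and relatedness are already collected. Data Collected lists no onset time for complications, so timing is given where known, or one before/after tick-box is added. Limiting the listing to what the form records avoids new follow-up for deaths. The downside is a slightly longer listing that includes events not due to the device.

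Optional: also send the DSMB, de-identified, the serious-event reports already made under Plan for Communication among IRB and Data safety monitoring. This would help with patients enrolled after the look, but it reaches events judged unrelated to the gauge only so far as those reports include them. The first section does not define association with the trial, and the study lead's further reports cover only events the sites have not reported. It also adds a forwarding and de-identification step under the data-sharing terms in Data Collection, so it costs more than the main change.
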